60	PegIFN- $\alpha$ 2a was not discontinued but the subject developed one of the following: - evidence of hepatic decompensation during treatment, or ALT increase clinically significant or accompanied by direct bilirubin increase -thyroid disorders or diabetes during treatment and cannot be controlled with medication - new or worsening ophthalmologic disorders - any deterioration of cardiovascular status - acute hypersensitivity reaction (e.g. urticaria, angioedema, bronchoconstriction, anaphylaxis) - serious infection (bacterial, viral, fungal) and sepsis - persistent or unexplained pulmonary infiltrates or pulmonary function impairment - onset or worsening of psoriatic lesion - moderate or severe depression (for mild depression, treatment discontinuation may be considered) - develops colitis symptoms (such as but not limited to abdominal pain, bloody diarrhea, and fever) - symptoms or signs suggestive of pancreatitis	Subject did not discontinue PegIFN- $\alpha$ 2a but developed one of the following: - evidence of hepatic decompensation during treatment, or ALT increase clinically significant or accompanied by direct bilirubin increase -thyroid disorders or diabetes during treatment and cannot be controlled with medication - new or worsening ophthalmologic disorders - any deterioration of cardiovascular status - acute hypersensitivity reaction (e.g. urticaria, angioedema, bronchoconstriction, anaphylaxis) - serious infection (bacterial, viral, fungal) and sepsis - persistent or unexplained pulmonary infiltrates or pulmonary function impairment - onset or worsening of psoriatic lesion - moderate or severe depression (for mild depression, treatment discontinuation may be considered) - develops colitis symptoms (such as but not limited to abdominal pain, bloody diarrhea, and fever) - symptoms or signs suggestive of pancreatitis	Developed withdrawal criteria but not withdrawn	Yes	Yes
61	In case of confirmed Grade 3 or Grade 4 hematologic abnormalities, discontinuation of investigational study treatment JNJ-3989 (and PegIFN- $\alpha$ 2a if applicable) should be considered. In case of discontinuation, NA treatment should be continued (see the description in Clinical Protocol Section 8.3.6.3)	Subject has confirmed Grade 3 or Grade 4 hematologic abnormalities, but discontinuation of study treatment was not considered	Developed withdrawal criteria but not withdrawn	Yes	Yes
62	Study procedure not done at scheduled visits, such as: Hematology Chemistry Blood coagulation Urine chemistry Urinalysis Pregnancy ECG Vital signs Physical Examination Liver Staging Ophthalmologic examination (including funduscopy) Testing for hepatitis A, B, C, D, and E virus, HIV-1 and -2b Serum IgM anti-HBc antibody test AFP test Hemoglobin A1c test TSH and T4	<enter study specific procedure(s)> <was/were> not done at <enter scheduled visit>	Other	If classified as major protocol deviation (reviewed case by case), excluded from PP set	No
63	Efficacy evaluation not done at scheduled visits, such as: HBV Virology Qualitative and quantitative HBsAg and HBeAg HBV DNA anti-HBs anti-HBe antibodies Fibroscan Ultrasound	<enter study specific efficacy evaluation(s)> <was/were> not done at <enter scheduled visit>	Other	If classified as major protocol deviation (reviewed case by case), excluded from PP set	No

64	Study Visits not performed, or Visit was not performed within the allowed window as per the protocol	<enter study visit> was not performed as per protocol schedule	Other	If classified as major protocol deviation (reviewed case by case), excluded from PP set	No
65	Usage of incorrect visit material (lab kits, etc )	Incorrect <enter incorrect visit material> was used	Other	If classified as major protocol deviation (reviewed case by case), excluded from PP set	No
66	Site reported protocol deviation not specified elsewhere	<enter reported protocol deviation not specified elsewhere>	Other	If classified as major protocol deviation (reviewed case by case), excluded from PP set	No
67	Blood and urine samples were collected (e g PK Samples) erroneously when should have not been collected and have not been subsequently destroyed (sample collected in error should be destroyed)	<enter blood or urine sample> sample were collected in error however not destroyed	Other	If classified as major protocol deviation (reviewed case by case), excluded from PP set	No

## **6.5. Appendix 5 Prior and Concomitant Medications**

Prior and Concomitant medications will be coded using the World Health Organization Drug Dictionary (WHO-DD). Prior medications are defined as any therapy used before the day of first dose (partial or complete) of study intervention. Concomitant medications are defined as any therapy used on or after the same day as the first dose of study intervention, including those that started before and continue on after the first dose of study intervention.

Summaries of concomitant medications will be presented by ATC class level 2, level 4 and preferred term, intervention arm, analysis phase and overall. The proportion of participants who receive each concomitant medication will be summarized as well as the proportion of participants who receive at least 1 concomitant medication.

Prior medications will be summarized by intervention arm and overall, and ATC class level 2, level 4 and preferred term.

**6.6. Appendix 6 Medical History**

A tabulation of the general medical history coded terms will be provided by body system class, intervention arm and overall.

## 6.7. Appendix 7 Intervention Compliance

Compliance will be summarized for the safety analysis set by intervention arm for each study agent (i.e. excluding NA).

Treatment compliance is defined as follows.

- For JNJ-3989: (Total number of injections received/7) \* 100%
- For PegIFN- $\alpha$ 2a: (Total number of injections received/ Total number of injections supposed to be receiveda) \* 100%

a For participants in Arm 1, a total of 24 injections should be administered. For participants in Arm 2 and 3, a total of 12 injections should be administered.

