4. STUDY DESIGN

4.1. Overall Design

This ISA describes a Phase 2 study of the combination regimen of JNJ-3989 with NA and different durations of PegIFN- α 2a, and with an immediate or delayed start of PegIFN- α 2a treatment. It is a companion document to the Master Protocol PLATFORMPAHPB2001, which describes the common design elements of the Platform study in participants with chronic HBV infection. This ISA describes specific and/or additional protocol elements applicable to this open-label, 3-arm, multicenter, interventional study to evaluate the efficacy, safety, tolerability, and PK of the combination of JNJ-3989, NAs, and PegIFN- α 2a in long-term (≥ 2 years of NA treatment) virologically suppressed, HBeAg-negative, chronic HBV-infected, adult participants.

Approximately 102 long-term (≥ 2 years of NA treatment) virologically suppressed, HBeAg-negative, chronic HBV-infected, adult participants, ≥ 18 (or the legal age of consent in the jurisdiction in which the study is taking place) to 65 years of age (inclusive) will be enrolled in this study.

This open-label study will be conducted in 3 periods:

- Screening Period (4 weeks [if necessary, eg, for operational reasons, can be extended to a maximum of 8 weeks decided on a case-by-case basis and in agreement with the Sponsor]).
- Treatment Period (24 weeks):
 - Arm 1 (N 34): JNJ-3989 for 24 weeks + NA for 24 weeks + PegIFN- α 2a for 24 weeks.
 - Arm 2 (N 34): JNJ-3989 for 24 weeks + NA for 24 weeks + PegIFN- α 2a from Week 12 till Week 24.
 - Arm 3 (N 34): JNJ-3989 for 24 weeks + NA for 24 weeks + PegIFN- α 2a from baseline till Week 12.
- Follow-up (FU) Period (48 weeks), starting at Week 24.

At baseline, participants who meet the eligibility criteria will be randomized in a 1:1:1 ratio to Arm 1, Arm 2, or Arm 3. Randomization will be stratified by absolute HBsAg level ($< 1,000$ IU/mL

versus $\geq 1,000$ IU/mL) at baseline and country grouping as proxy for HBV genotype (GT) at enrollment, with 3 levels: Poland (predominantly GT-A) versus Russia (predominantly GT-D) versus all other countries (other or mixed GT prevalence) (Kim 2011). Participants in Arm 2 who no longer meet the PegIFN- α 2a eligibility criteria (see Exclusion Criterion A24 in Section 5.2, Exclusion Criteria) at Week 12, based on available laboratory or clinical data, will continue JNJ-3989 and NA treatment until Week 24 without PegIFN- α 2a.

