### 5.6.1. Extent of Exposure

The number and percentage of participants who receive each study agent within a study intervention will be summarized.

Descriptive statistics for duration of each study agent within a study intervention (N, mean, SD, median, and range (minimum, maximum)) during the treatment period will be summarized. The duration of treatment with NA will be also summarized for the follow-up phase by intervention arm.

Because of the different route and frequency of treatment administration across the 3 agents (for JNJ-3989 one subcutaneous injection once every 4 weeks, for PegIFN- $\alpha$ 2a one subcutaneous injection weekly and for NA once daily tablet) the total duration for each study treatment as follows:

- JNJ-3989:  $[\text{Min} ((\text{Date of last JNJ-3989 injection in the given phase} + 27 \text{ days}), \text{Date of discontinuation from JNJ-3989}, \text{Date of trial disposition}, \text{cut-off date}) - \text{Date of first JNJ-3989 injection in the given phase} + 1] / 7$
- PegIFN- $\alpha$ 2a:  $[\text{Min} (\text{Date of the last PegIFN-}\alpha\text{2a injection} + 6 \text{ days}, \text{Date of discontinuation from PegIFN-}\alpha\text{2a}, \text{Date of trial disposition}, \text{cut-off date}) - \text{Date of first PegIFN-}\alpha\text{2a injection} + 1] / 7$
- NA:  $[\text{Min} (\text{Date of the last NA administration in the given phase}, \text{Date of discontinuation from NA}, \text{Date of trial disposition}, \text{Date of clinical cut-off}) - \text{Date of first NA administration date in the given phase} + 1] / 7$

For NA treatment, the total duration of exposure will be calculated separately for treatment period and FU phases. For FU, the total duration will add up the weeks of NA treatment post-treatment period for those participants during the NA re-treatment weeks. Those participants who never restarted NA treatment after Week 24 will be counted as having zero weeks of NA exposure during the FU.

Cutoff dates will be defined to match the prespecified timepoints for interim analyses and the primary analysis, respectively (Section 5.8).

The number and percentage of participants who skipped any dose of JNJ-3989 or PegIFN- $\alpha$ 2a or NA will be summarized separately for each study intervention by intervention arm during the

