treatment period. Additionally, the number and percentage of participants who missed 2 or more JNJ-3989 injections, or who missed more than 5 doses of NA within a four-week period or who missed 2 or more PegIFN- $\alpha$ 2a injections will be presented.

Study intervention compliance will be summarized descriptively. See [Appendix 7](#) for further details.

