### 5.8.3.3. Overview of Data Reviews, Interim, Primary and Final Analyses

The overview of data domains and specific endpoints that will be provided to the DRC for review is presented in [Table 10](#). Details on the type of summaries and analyses of both efficacy and safety variables are described in the following sections.

**Table 10: Overview of Data Summaries and Analyses to be Provided to the DRC at Data Reviews, Interim, Primary and Final Analyses**

	DR1/ Week 4 (approx. N=51)	DR approx. every 8 weeks	IA1/ Week 12 (approx. N=51)	IA2/ Week 24 (N=51)	Primary/ Week 24 (approx. N=102)	IA3/ Week 36 (N=102)	IA4/ Week 48 (N=102)	IA5/ Week 60 (N=102)	Final analysis/ Week 72 (N=102)
Subject information									
Baseline & Demographic characteristics	X	X	X	X	X	X	X	X	X
Disposition and Study Populations	X	X	X	X	X	X	X	X	X
Extend of Exposure	X	X	X	X	X	X	X	X	X
Safety									
TEAEs, SAEs, AE of special interest, fatal AEs, AEs causing treatment discontinuation	X	X	X	X	X	X	X	X	X
Laboratory tests	X	X	X	X	X	X	X	X	X
ECG	X	X	X	X	X	X	X	X	X
Vital signs	X	X	X	X	X	X	X	X	X
Efficacy									
Values and Changes over time in HBsAg, HBeAg, HBV DNA and ALT		X	X	X	X	X	X	X	X
Proportion of participants with HBsAg, HBeAg, HBV DNA and ALT below/above different cutoffs		X	X	X	X	X	X	X	X
Other secondary efficacy endpoints			X	X	X	X	X	X	X
Exploratory endpoints			X	X	X	X	X	X	X

	DR1/ Week 4 (approx. N=51)	DR approx. every 8 weeks	IA1/ Week 12 (approx. N=51)	IA2/ Week 24 (N=51)	Primary/ Week 24 (approx. N=102)	IA3/ Week 36 (N=102)	IA4/ Week 48 (N=102)	IA5/ Week 60 (N=102)	Final analysis/ Week 72 (N=102)
Virologic breakthrough	X	X	X	X	X	X	X	X	X
Flares: Viral, Biochemical, Clinical	X	X	X	X	X	X	X	X	X
PK*			X	X	X	X	X	X	X
*If there are available data, it will be analyze.									

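### The compliance percentage in SAP Appendix 7 divides by the full planned course for everyone, so it mixes adherence with treatment truncation, and for PegIFN-α2a this can differ by arm

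*SAP*

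**What the plan says.** SAP 6.7 (Appendix 7) summarises compliance by arm in the safety set, for JNJ-3989 and PegIFN-α2a but not NA. The JNJ-3989 rule is "For JNJ-3989: (Total number of injections received/7) \* 100"%. For PegIFN-α2a the denominator is described as the number of injections the participant should have had, but a footnote fixes it by arm: "For participants in Arm 1, a total of 24 injections should be administered", and "For participants in Arm 2 and 3, a total of 12 injections should be administered". Nothing in the appendix adjusts for data cut-off, discontinuation or ineligibility, and no analysis phase is named.

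Compliance is called from SAP 5.6.1, Extent of Exposure: "Study intervention compliance will be summarized descriptively". That section caps the injectable-exposure durations at discontinuation of the agent, trial disposition and cut-off, and adds: "Cutoff dates will be defined to match the prespecified timepoints for interim analyses and the primary analysis, respectively". SAP 5.8.3.3, Table 10, marks a row "Extend of Exposure" at every data review, every interim analysis, the primary analysis and the final analysis.

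Protocol 4.1 provides that Arm 2 participants who no longer qualify for PegIFN-α2a at Week 12 "will continue JNJ-3989 and NA treatment until Week 24 without" it. Protocol 7.1 stops PegIFN-α2a when JNJ-3989 is stopped early, and lists events that require PegIFN-α2a to be discontinued.

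**The concern.** A compliance figure should say how much of what was due was taken. With a fixed full-course denominator, three kinds of injection that were not due are counted as not taken:

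- PegIFN-α2a injections for Arm 2 participants who fail the Week 12 re-check;
- injections after a protocol-directed or other early stop;
- injections scheduled after the data cut-off.

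The trial compares PegIFN-α2a schedules. A by-arm compliance table is one place a reader looks to see whether a difference at Week 24 reflects the schedule or how well it was followed. PegIFN-α2a is given early in Arm 3 and late in Arm 2, so truncation at the same calendar week removes different shares of the course.

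**Working it through.** **Inputs.** Protocol 1.3 (Schedule of Activities and its PegIFN-α2a footnote) gives JNJ-3989 at Weeks 0, 4, 8, 12, 16, 20 and 24. PegIFN-α2a is weekly over Weeks 0–23 (Arm 1), 12–23 (Arm 2) and 0–11 (Arm 3). SAP 3 gives 34 per arm and an attrition allowance of about 10%.

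**Reproducing the plan's totals.** Counting these schedules gives 7 JNJ-3989 injections, and 24, 12 and 12 PegIFN-α2a injections. They match Appendix 7. The totals are right; the question is whom they are applied to. In all the cases below, nobody misses an injection that was due.

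**(a) Arm 2, ineligible at Week 12.** Received 0, denominator 12, score 0%. The safety set needs only one dose of any study agent, so these participants stay in the table. Each lowers the Arm 2 mean by 1/34 = 2.9 points, against 100% had the course been given.

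**(b) Early exit from all injections, primary or final analysis.** Assume 10% stop at a time uniform over Weeks 0–24, equally in each arm. Mean share of the PegIFN-α2a course received among those who stop:

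- Arm 1: 12.5/24 = 0.521
- Arm 2: half stop before Week 12 and receive none; the rest average 6.5/12 = 0.542. Mean 0.5 × 0 + 0.5 × 0.542 = 0.271
- Arm 3: half stop before Week 12 and average 0.542; the rest have finished. Mean 0.5 × 0.542 + 0.5 × 1 = 0.771

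Arm mean = 0.9 + 0.1 × share:

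| | Arm 1 | Arm 2 | Arm 3 |
|---|---|---|---|
| Stopping uniform over Weeks 0–24 | 95.2% | 92.7% | 97.7% |
| Stopping uniform from first PegIFN-α2a dose | 95.2% | 95.4% | 95.4% |

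The second row uses 12.5/24 for Arm 1 and 6.5/12 for Arms 2 and 3. The ordering in the first row therefore depends on when people stop. For JNJ-3989 the first-row assumption gives 0.9 + 0.1 × 3.5/7 = 95.0% in every arm.

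**(c) Looks before everyone has passed Week 24.** A fully adherent, ongoing participant, with that week's injection counted:

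| | JNJ-3989 | PegIFN-α2a Arm 1 | Arm 2 | Arm 3 |
|---|---|---|---|---|
| Week 4 | 2/7 = 29% | 5/24 = 21% | 0/12 = 0% | 5/12 = 42% |
| Week 12 | 4/7 = 57% | 13/24 = 54% | 1/12 = 8% | 12/12 = 100% |

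Real misses can be hidden: at Week 11 an Arm 3 participant who has missed 3 of 12 shows 9/12 = 75%, while an Arm 1 participant who has missed none shows 12/24 = 50%.

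**Counting phase.** SAP Table 3 ends the treatment period the day before the Week 24 intake. If compliance were counted within that phase, the JNJ-3989 maximum would be 6/7 = 86%.

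**With injections due as the denominator.** Everyone in (b) and (c) who was due at least one injection scores 100%. Arm 2 participants who were due none drop out of the percentage.

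**The case against.** The strongest case against has several parts.

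- *Other measures sit nearby.* SAP 5.6.1 separately counts participants who skipped any dose and those who missed two or more injections of JNJ-3989 or of PegIFN-α2a, and gives capped durations. SAP 5.2 reports discontinuations with reasons. This stands as mitigation, but it does not correct a by-arm percentage labelled compliance.
- *Nothing inferential depends on the ratio.* Missed-dose deviations enter the per-protocol set and the intercurrent events through case review under Table 13. This stands.
- *Received over planned is useful.* It shows how much of the regimen was delivered, whereas received over due gives 100% to someone who stops after one injection. This stands, and is why both should be reported.

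Some stronger readings are tempting, but the documents do not support them.

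- A reader might infer that the table measures truncation in place of adherence. For participants who complete treatment as planned, it is adherence.
- A reader might infer that Arm 2 is ranked lowest and Arm 3 highest by construction. That order needs stopping spread over calendar weeks. Stops specific to PegIFN-α2a can occur only after it starts, and under the second row of (b) there is no such ordering.
- A reader might infer a gap of 10 to 14 points between Arms 3 and 2. That needs 5% or 10% of Arm 2 to be ineligible at Week 12 (92.7 × 0.95 = 88.1%; 92.7 × 0.90 = 83.4%; against 97.7%), and no document gives such a rate.
- A reader might extend the arm distortion to JNJ-3989. Its schedule and denominator are the same in every arm, so it is understated similarly unless stopping or follow-up differs.
- A reader might take it as settled that the data review committee will see the figures in (c). Table 10 names exposure, not compliance.

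**Conclusion.** The point holds in a limited form. The Appendix 7 percentage mixes adherence with truncation, and conflicts with the plan's own provision for Arm 2 participants who go on without PegIFN-α2a.

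- The Week 12 effect needs no modelling assumption beyond a 34-person arm: about 2.9 points per ineligible participant.
- The spread at the primary or final analysis is about 5 points (97.7 − 92.7). It rests on 10% stopping, a figure SAP 3 gives as a sample-size allowance and not as a PegIFN-α2a stopping rate, and on stopping being uniform in calendar time and equal across arms.
- The cut-off effect is large for an individual, but it is confined to looks before all participants have passed Week 24 (the first and early data reviews and the first two interim analyses). It also rests on compliance being shown there, which is inferred from its place in 5.6.1 and the exposure row of Table 10. By the primary analysis everyone has completed Week 24 or discontinued, so cut-off no longer matters.

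The arm distortion concerns PegIFN-α2a. No primary inference changes. Priority is minor to moderate.

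**What to change.** In Appendix 7:

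1. Define compliance as injections received divided by injections scheduled from the first planned dose of that agent to the earliest of discontinuation of that agent, study discontinuation and cut-off. These are the limits 5.6.1 already uses for exposure.
2. Report PegIFN-α2a compliance as not applicable for Arm 2 participants never due it (stopped before Week 12, or ineligible at the Week 12 re-check), and show their number.
3. Report the present ratio alongside, relabelled as percentage of planned course received, so that early stopping remains visible.
4. State the counting phase so that the Week 24 JNJ-3989 injection is included.
5. Say in Table 10 whether compliance is part of the exposure outputs at data reviews and interim analyses.

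The cost is SAP wording, one derived variable built from dates already needed for exposure, and an extra table row.

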## 6.8. Appendix 8 Adverse Events of Special Interest

Adverse events of special interest list of MedDRA preferred terms.

**Table 14: Adverse Events of Special Interest and Preferred Terms**

Adverse Event of Special Interest	Source	Preferred Term
ALT/AST elevation	(Modified) Liver related investigations, signs and symptoms (SMQ) narrow, (MedDRA v23.1)	Alanine aminotransferase abnormal  Alanine aminotransferase increased Aspartate aminotransferase abnormal Aspartate aminotransferase increased Hepatic enzyme abnormal Hepatic enzyme increased Hepatic function abnormal Hypertransaminasaemia Liver function test abnormal Liver function test increased Transaminases abnormal Transaminases increased
Renal Complications	Acute renal failure (SMQ) narrow (MedDRA v23.1)	Acute kidney injury  Acute phosphate nephropathy Anuria Azotaemia Continuous haemodiafiltration Dialysis Foetal renal impairment Haemodialysis Haemofiltration Neonatal anuria Nephropathy toxic Oliguria Peritoneal dialysis Prerenal failure Renal failure Renal failure neonatal Renal impairment Renal impairment neonatal Subacute kidney injury
	Acute renal failure (SMQ) broad (MedDRA v23.1)	Albuminuria

---

	Blood creatinine abnormal
	Blood creatinine increased
	Blood urea abnormal
	Blood urea increased
	Blood urea nitrogen/creatinine ratio increased
	Creatinine renal clearance abnormal
	Creatinine renal clearance decreased
	Creatinine urine abnormal
	Creatinine urine decreased
	Crystal nephropathy
	Fractional excretion of sodium
	Glomerular filtration rate abnormal
	Glomerular filtration rate decreased
	Hypercreatininaemia
	Hyponatriuria
	Intradialytic parenteral nutrition
	Kidney injury molecule-1
	Nephritis
	Neutrophil gelatinase-associated lipocalin increased
	Oedema due to renal disease
	Protein urine present
	Proteinuria
	Renal function test abnormal
	Renal transplant
	Renal tubular disorder
	Renal tubular dysfunction
	Renal tubular injury
	Renal tubular necrosis
	Tubulointerstitial nephritis
	Urea renal clearance decreased
	Urine output decreased
Tubulointerstitial diseases narrow (MedDRA v23.1)	Acidosis hyperchloraemic
	Acquired aminoaciduria
	Acute phosphate nephropathy
	Aminoaciduria
	Beta-N-acetyl-D-glucosaminidase increased
	Crystal nephropathy
	Eosinophils urine present
	Fanconi syndrome acquired
	Hyperphosphaturia
	Isosthenuria
	Metabolic nephropathy
	Nephritis allergic

---

		Nephrogenic diabetes insipidus
		Nephropathy toxic
		Renal glycosuria
		Renal papillary necrosis
		Renal phospholipidosis
		Renal tubular acidosis
		Renal tubular atrophy
		Renal tubular disorder
		Renal tubular dysfunction
		Tubulointerstitial nephritis
		Tubulointerstitial nephritis and uveitis syndrome
		Urine phosphorus increased
		Urine retinol binding protein increased
	Tubulointerstitial diseases broad (MedDRA v23.1)	Albumin urine present
		Albuminuria
		Blood chloride increased
		Blood uric acid decreased
		Crystal urine present
		Crystalluria
		Cylindruria
		Haematuria
		Haemoglobin urine present
		Haemoglobinuria
		Hypercalcaemic nephropathy
		Hyperchloraemia
		Kidney fibrosis
		Kidney small
		Microalbuminuria
		pH urine abnormal
		pH urine increased
		Polyuria
		Potassium wasting nephropathy
		Protein urine present
		Proteinuria
		Red blood cells urine positive
		Renal atrophy
		Renal tubular injury
		Renal tubular necrosis
		Sterile pyuria
		Urinary casts present
		Urine phosphorus abnormal
		Aplastic anaemia
Hematologic abnormalities	(Modified) Haematopoietic cytopenias affecting more than one type of blood cell (SMQ), (MedDRA v23.1)	

---

	Autoimmune aplastic anaemia
	Bicytopenia
	Bone marrow failure
	Cytopenia
	Febrile bone marrow aplasia
	Full blood count decreased
	Gelatinous transformation of the bone marrow
	Immune-mediated pancytopenia
	Pancytopenia
	Panmyelopathy
	Aspiration bone marrow abnormal
	Biopsy bone marrow abnormal
	Blood count abnormal
	Blood disorder
	Bone marrow disorder
	Bone marrow infiltration
	Bone marrow myelogram abnormal
	Bone marrow necrosis
	Bone marrow toxicity
	Haematotoxicity
	Myelodysplastic syndrome
	Myelodysplastic syndrome transformation
	Myelofibrosis
	Myeloid metaplasia
	Plasmablast count decreased
	Scan bone marrow abnormal
(Modified) Haematopoietic erythropenia (SMQ), (MedDRA v23.1)	Aplasia pure red cell
	Aplastic anaemia
	Erythroblast count decreased
	Erythroid maturation arrest
	Erythropenia
	Hypoplastic anaemia
	Microcytic anaemia
	Proerythroblast count decreased
	Red blood cell count decreased
	Reticulocyte count decreased
	Reticulocytopenia
	Anaemia
	Erythroblast count abnormal
	Erythropoiesis abnormal
	Haematocrit abnormal
	Haematocrit decreased

---

	Haemoglobin abnormal
	Haemoglobin decreased
	Leukoerythroblastic anaemia
	Normochromic anaemia
	Normochromic normocytic anaemia
	Normocytic anaemia
	Proerythroblast count abnormal
	Red blood cell count abnormal
	Reticulocyte count abnormal
	Reticulocyte percentage decreased
(Modified) Haematopoietic leukopenia (SMQ), (MedDRA v23.1)	Agranulocytosis
	Band neutrophil count decreased
	Band neutrophil percentage decreased
	Basophil count decreased
	Basophilopenia
	B-lymphocyte count decreased
	Cyclic neutropenia
	Eosinopenia
	Eosinophil count decreased
	Febrile neutropenia
	Granulocyte count decreased
	Granulocytes maturation arrest
	Granulocytopenia
	Idiopathic neutropenia
	Leukopenia
	Lymphocyte count decreased
	Lymphopenia
	Metamyelocyte count decreased
	Monoblast count decreased
	Monocyte count decreased
	Monocytopenia
	Myeloblast count decreased
	Myelocyte count decreased
	Neutropenia
	Neutropenic infection
	Neutropenic sepsis
	Neutrophil count decreased
	Promyelocyte count decreased
	Pure white cell aplasia
	T-lymphocyte count decreased
	White blood cell count decreased
	Basophil count abnormal

---

	Basophil percentage decreased
	B-lymphocyte abnormalities
	B-lymphocyte count abnormal
	Differential white blood cell count abnormal
	Eosinophil count abnormal
	Eosinophil percentage decreased
	Full blood count abnormal
	Granulocytes abnormal
	Leukopenia neonatal
	Lymphocyte count abnormal
	Lymphocyte percentage abnormal
	Lymphocyte percentage decreased
	Monocyte count abnormal
	Monocyte percentage decreased
	Mononuclear cell count decreased
	Myeloblast percentage decreased
	Myelocyte percentage decreased
	Myeloid maturation arrest
	Neutrophil count abnormal
	Neutrophil percentage decreased
	Plasma cell disorder
	Plasma cells absent
	White blood cell analysis abnormal
	White blood cell count abnormal
	White blood cell disorder
(Modified) Haematopoietic thrombocytopenia (SMQ), (MedDRA v23.1)	Acquired amegakaryocytic thrombocytopenia
	Megakaryocytes decreased
	Platelet count decreased
	Platelet maturation arrest
	Platelet production decreased
	Platelet toxicity
	Thrombocytopenia
	Megakaryocytes abnormal
	Platelet count abnormal
	Platelet disorder
	Plateletcrit abnormal
	Plateletcrit decreased

